14.3 Confidentiality

The Principal Investigator has a responsibility to ensure that participant anonymity is protected and maintained. They must also ensure that their identities are protected from any unauthorised parties. Information with regards to study participants will be kept confidential and managed in accordance with the Data Protection Act, the General Data Protection Regulation (GDPR), NHS Caldecott Principles, the UK Policy Framework for Health and Social Care Research, and the conditions of Research Ethics Committee favourable opinion. All research team members have undergone GCP training. The Chief Investigator and the study team will adhere to these parameters to ensure that the Participant's identity is protected at every stage of their participation within the study.

Following consent and during the study, all participant study records and samples will be marked by a single, unique pseudoanonymised identifier. The code for the pseudoanonymised will be kept on a study ID log with the ISF, which will be kept within a locked filing cupboard within a locked room that only the researchers involved have access to. A paper record of any information will be coded and any patient identifiable information (PID) will be removed e.g. name, date of birth and NHS number.

Personal information will only be used on the consent form and the pseudoanonymisation code (screening log). Personal information will be used by the site study team to contact participants if needed and to remind participants of study dates. Fully anonymised data will be shared with fellow researchers via conference presentation and via publication of the results in scientific journals. Pseudoanonymised data will be shared between the research teams named in the application, and access will be granted to members of the Sponsor and Barts CVCTU teams for the purposes of data monitoring and audit.

Only the clinical care team will have access to clinical case notes, which have identifiable personal information for the purposes of identifying potential participants.

The research team will create a separate study file for each participant which will comprise of information given by the participant at the time of screening and during

visits. Routine biochemistry will be measured in Barts Health NHS Trust clinical laboratory by the laboratory biochemists.

The Investigator Site File (ISF) and subject study files will be kept in a locked cupboard in a locked room that only the researchers involved have access to. The Trial Master File (TMF) will be maintained and stored by the Barts CVCTU in the William Harvey Heart Centre, in a locked room with restricted access.

Under no circumstances will non-encrypted named data be placed on a laptop computer, portable storage device (memory stick or CD-ROM) or transferred by email.

14.4 Record Retention and Archiving

Data will be managed with reference to the Barts CTU SOP 'Data Management'. During the course of research, all records are the responsibility of the Chief Investigator and must be kept in secure conditions. The UK Policy Framework for Health and Social Care Research requires that research records are kept for 20 years after the project has completed. For studies involving Barts Health NHS Trust patients, undertaken by Barts Health NHS Trust staff, or sponsored by Barts Health NHS Trust or Queen Mary, University of London, the approved repository for long-term storage of local records is the Trust Corporate Records Centre. Both electronic and paper documentation will be retained in physical form for archiving. Sponsor approval will be requested prior to final destruction of the trial records.

15. Laboratories

15.1 Central and local laboratories

Biochemical and haematology assays will be performed in the pathology labs of the Barts Health NHS Trust. Blood samples will be taken at the screening visit, and these are standard blood tests to assess baseline characteristics of the participant and confirm eligibility.

15.2 Sample collection and preparation

Blood tubes will be labelled with the following information:

- Subject Number
- Date of Collection
- Sampling Time (nominal)
- Study Name

16. Interventions and tools

16.1 Devices

Loop recorder	• Manufacturer: MEDTRONIC LTD
----------------------	-------------------------------

	
 • Indication : Long-term monitoring of heart rhythm. Determination of duration of AF episodes and confirmation of primary endpoint • CE Mark : Yes • Source of Device : Medtronic Ltd In-kind research grant contribution • How device used : The Reveal device is inserted in the prepectoral position under the skin. This is performed with local anaesthetic in the preadmission clinic by a trained nurse or doctor. The device will provide a continuous recording of the heart rhythm and rate, and will be able to download duration of AF episodes via a home monitoring system to establish the primary endpoint of the study.
Cryoballoon, Cryocath, Achieve wire, Console and related items	
 • Manufacturer: MEDTRONIC • Indication: AF ablation catheter and sheath • CE Mark: Yes • Source of Device: Clinical use for AF ablation • How device used: The cryoballoon is the key specified technique for performing pulmonary vein isolation in the ablation arm in this trial. This allows the physician electrophysiologist to perform a circumferential freeze around the pulmonary veins to electrically isolate the vein, thus preventing pulmonary vein ectopy from triggering arrhythmia.

16.2 Techniques and interventions

Conscious sedation or GA administered and sterile field prepared. 8F and 7F sheaths placed in RGV under ultrasound guidance.

16.2.1 PVI group

Transeptal puncture (TSP) done using standard techniques using operator preference equipment. Heparin given as per local protocol. Change TSP sheath over-the-wire to cryosheath. Achieve wire through cryoballoon and cryoballoon placed in LA through cryosheath. Cryoablation to LSPV, RIPV, RSPV, LLPV, with phrenic pacing via quadripolar catheter via 7F sheath during right sided lesions. Isolation confirmed with electrograms in veins. Veins considered isolated if sudden loss of electrogram signal, or if pacing through all poles of achieve catheter is able to produce electrical capture of vein but not of LA. Termination of freeze if loss of phrenic capture, vein temperature < -60°C, or operator decision for termination. Isolation was considered indeterminate if unable to confirm signal loss or electrical capture. At end of isolation, DCCV performed (if patient still in AF). Sheath withdrawal, Femostop haemostasis and protamine as per local protocol.

REVEAL-LINQ insertion will be performed at the end of the case. Prepectoral area will be cleaned and any overlying ECG leads removed. 10mls of local anaesthetic will be infiltrated to the skin and the device injected under the skin in a sterile manner. The incision will be closed according to local practice.

16.2.2 DCCV group

Sedation maintained for 30 minutes. At 30 minutes, sedation optimised and DCCV performed. Sheath withdrawal, Femostop haemostasis and protamine as per local protocol.

REVEAL-LINQ insertion will be performed at the end of the case. Prepectoral area will be cleaned and any overlying ECG leads removed. 10mls of local anaesthetic will be infiltrated to the skin and the device injected under the skin in a sterile manner. The incision will be closed according to local practice.

16.2.3 All patients

Recovered to ward. 12 lead ECG performed but not shown to patient. Patient mobilised and discharged after 4 hours. The cardiac physiologist will register the patient for remote monitoring, a physiologist will show the patient how to use their monitoring station.

16.3 Tools

16.3.1 Questionnaires:

Short Form (SF 12) The short form health survey

This is a shorter version of the SF-36 and consists of 12 questions. It is comparable with the SF-36 especially for the physical component summary (PCS) and mental component summary (MCS). This test gives more precision than the EQ-5D and has been extensively validated in general and also in cardiac populations (De Smedt, Clays, Annemans, & De Bacquer, 2014).

Atrial Fibrillation Specific Patient Reported Outcome Measure (AF PROMS)

This 28 item inventory measures how AF has impacted the patient's quality of life. It assesses how much the patient has been concerned by specific symptoms and how AF has impacted their emotional state and daily activities. This inventory was developed at Barts and has been validated by [name] (unpublished PhD thesis).

16.4 Medicinal product

- Heparin given as per local AF ablation protocol

16.5 Antiarrhythmic drugs

Physicians will be encouraged to use anti-arrhythmic drugs in the periprocedural period, such as Amiodarone 200mg tds in a reducing dose commencing at least 2 weeks prior to index procedure. Choice of antiarrhythmic medication will be at the discretion of the patient's physician and will be recorded on the CRF. Participating centres will be encouraged to follow local centre periprocedural guidelines for antiarrhythmic medication for AF ablation for all patients

17. Safety reporting

17.1 Adverse Events (AEs)

An AE is any untoward medical occurrence in a participant to whom an intervention has been administered, including occurrences which are not necessarily caused by or related to that intervention. An AE can therefore be any unfavourable or unintended sign (including an abnormal laboratory finding), symptom or disease temporally associated with study activities.

17.2 Adverse Reaction (ARs)

An AR is any untoward and unintended response in a participant to an intervention. All adverse events judged by either the reporting investigator or the sponsor as having a reasonable causal relationship to the intervention qualify as adverse reactions. The expression 'reasonable causal relationship' means in general that there is evidence or an argument to suggest a causal relationship.

17.3 Notification and reporting of Adverse Events and Reactions

If the AE is not defined as serious, the AE will be recorded in the study documents and the participant followed up by the research team. The AE will be documented in the participants' source documents, the Case Report Form (CRF), and, where appropriate, medical records.

The following events will be considered and reported as Adverse Events, and not serious adverse events, as they are expected as known complications of procedures:

- Phrenic nerve damage
- Tamponade or pericardial effusion
- Haematoma
- Skin Burns
- Chest pain
- Groin vascular complications.

The period for adverse events reporting will be from the signing of consent until the end of study visit at 12 month follow-up.

17.4 Serious Adverse Events (SAEs) or reactions

A serious adverse event (SAE) is defined as an untoward occurrence that:

- Results in death,
- Is life-threatening,
- Requires hospitalisation or prolongation of existing hospitalisation,
- Results in persistent or significant disability or incapacity,
- Consists of a congenital anomaly or birth defect, or
- Is otherwise considered medically significant by the investigator.

SARs will be reported to the REC where in the opinion of the Chief Investigator the event was serious and:

- Related (it may have resulted from administration of any of the research interventions), and
- Unexpected (the type of event is not listed in the protocol or other Reference Safety Information as an expected occurrence).

17.5 Notification and reporting of Serious Adverse Events

Serious Adverse Events (SAEs) that are considered to be 'related' and 'unexpected' will be reported to the sponsor within 24 hours of learning of the event, and to the REC within 15 days in line with the required timeframe.

The treatment code for the participant will be broken when reporting an 'unexpected and related' SAE. The unblinding of individual participants by the PI / CI in the course of a clinical study will only be performed if necessary for the safety of the study participant.

17.6 Urgent Safety Measures

The CI will take urgent safety measures if necessary to ensure the safety and protection of the clinical study participant from immediate hazards to their health and safety. The measures will be taken immediately. The approval of the REC prior to implementing urgent safety measures is not required. However the CI will inform the sponsor and Research Ethics Committee (via telephone) of this event immediately.

The CI will inform the REC in writing within 3 days, in the form of a substantial amendment. The sponsor (Joint Research Management Office (JRMO)) will be sent a copy of the correspondence with regards to this matter.

17.7 Annual Safety Reporting

The CI will send the Annual Progress Report to the REC using the HRA template (the anniversary date is the date on the REC "favourable opinion" letter) and to the sponsor.

17.8 Overview of the Safety Reporting responsibilities

The CI is the medical assessor on behalf on the sponsor and will review all events reported. The CI will ensure that safety monitoring and reporting is conducted in accordance with the sponsor's requirements.

The CVCTU team will maintain safety reporting responsibilities on behalf of the Sponsor, following the JRMO SOP 26b – Safety reporting for non-CTIMPs and using the SAE template to capture SAEs electronically via REDCap, and the Investigator teams will report all SAEs to the CVCTU, and the CVCTU will ensure adherence to the Sponsor safety reporting requirements.

For the purposes of this protocol, a 'serious breach', is a breach which is likely to effect to a significant degree:

- The safety or physical or mental integrity of the participants of the trials; or
- The scientific value of the trial.

The CI is responsible for reporting any serious breaches to the sponsor (JRMO) **within 24 hours**. The sponsor will notify and report to REC within 7 working days of becoming aware of the serious breach.

These non-compliances may be captured from a variety of different sources including monitoring visits, CRFs, communications and updates. The CVCTU will maintain a log of the non-compliances identified and reported to them, and these will be maintained on a site Deviation log. The CVCTU will action a timeframe in which they need to be dealt with, and each action will be given a different timeframe dependent on the severity. If the actions are not dealt with accordingly, they will be escalated to the Sponsor, who will confirm an appropriate action, which may include an on-site audit.

18. Monitoring and auditing

The sponsor or delegate retains the right to audit any study, study site, or central facility. Any part of the study may be audited by the funders, where applicable.

The trial will be monitored with reference to the Barts CTU SOP Monitoring. A trial specific monitoring plan will be developed by the CVCTU and determined by a formal risk assessment. The Study team will be initiated and monitored in accordance with the sponsor SOPs led by the Barts CVCTU, who will provide overall study management. A CVCTU monitor will conduct on-site monitoring visits, and be the primary contact for the research team in relation to study queries, including those related to source data and data capture, safety reporting, and participant recruitment and follow-up activities.

The CVCTU Project Manager is responsible for creating the trial specific monitoring plan, to ensure adequate monitoring of the trial and that both on-site and central monitoring is conducted to verify that source data is accurate, reliable and complete.

The CVCTU will have its own audit schedule for trials on their portfolio. A study may be identified for audit by any method listed below:

1. A project may be identified via the risk assessment process.
2. An individual investigator or department may request an audit.
3. A project may be identified via an allegation of research misconduct or fraud or a suspected breach of regulations.
4. Projects may be selected at random. The Department of Health states that Trusts should be auditing a minimum of 10% of all research projects.
5. Projects may be randomly selected for audit by an external organisation.

Internal audits may be conducted by a sponsor's or funder representative.

19. Trial committees

Trial Steering Committee

A Trial Steering Committee (TSC) will be established to review and monitor all aspects of the conduct and progress of the trial, ensuring that the protocol is adhered to, appropriate action is taken to safeguard the twenty participants and the quality of the

trial maintained. The TSC will be composed of two independent experts in the field of electrophysiology with experience in clinical trials along with the investigators and the trial manager. A medical statistician will join the TSC to provide expertise in clinical trials and one lay members of the committee will be appointed. This committee would meet before patient recruitment and then quarterly to assess safety, feasibility or any other arising problems (e.g. with recruitment) and their recommendations will be followed.

The TSC will meet on a monthly basis, and will include the following:

- An independent/external Chair
- One independent/external collaborator who will participate in the larger trial
- CI/PI
- Statistician
- Trial Manager
- Patient representative

Data Monitoring and Safety Committee

An independent Data and Safety and Monitoring Committee (DSMC) will be formed to monitor patient safety as the study progresses. The DSMC has been selected by and communicates directly to the study's TSC. There will be an independent chair of this committee, an independent member with clinical cardiovascular trials expertise, and other members of the trial management group, including the PI, statistician, and trial manager will attend open sessions. The DSMC will meet prior to initiation of the clinical study, after the recruitment of 4 patients and then at 3 monthly intervals. The DSMB will have access to unblinded patient data. If a serious concern with the safety of the patients in the trial would arise, the DSMC may recommend early termination of the study.

20. Finance and funding

Funding for the study has been provided by the Barts Charity and with support from Medtronic, who are providing the REVEAL devices for the trial.

21. Indemnity

The NHS indemnity scheme will apply. It provides cover for the design, management, and conduct of the study.

22. Dissemination of research findings

All relevant data from this study will be submitted to peer review journals for publication following the termination of the study in line with sponsor and trust publication policy.

23. References

13	Safety analysis.....	16
13.1	Adverse events (AE)	16
13.2	Deaths or serious adverse events (SAE)	16
14	Presentation of analysis	17
15	REFERENCES	23

4 GLOSSARY of Terms and Abbreviations

AE	Adverse event
AF	Atrial Fibrillation
BMI	Body Mass Index
BP	Blood Pressure
CHADS	Score for estimating AF stroke risk
CI	Confidence Interval
DBP	Diastolic Blood Pressure
DC	Direct Current
DCCV	Direct Current Cardioversion
DSMC	Data and Safety Monitoring Committee
ECG	Electrocardiogram
FU	Follow-up
HR	Heart Rate
IQR	Interquartile Range
LA	Left Atrial
LINQ	Reveal LINQ cardiac monitoring system
LVEF	Left Ventricular Ejection Fraction
MCS	Mental Health Composite Scale (SF-12)
MI	Myocardial infarction
BI	Blinding Index
OR	Odds Ratio
PCI	Percutaneous Coronary Intervention
PCS	Physical Health Composite Scale (SF-12)
PROMS	Patient Reported Outcome Measures
PVI	Pulmonary Vein Isolation
QoL	Quality of Life
R	“R” Statistical Programming Software
SAE	Serious Adverse Event
SAP	Statistical Analysis Plan
SF-12	Twelve item short form survey
SBP	Systolic Blood Pressure
SD	Standard Deviation

5 Introduction

This SAP has been written based on information from the study protocol version 2.0, dated 25/06/2019.

5.1 Preface

Cardioversion with antiarrhythmic medication is commonly used as a first-line rhythm control strategy for patient with persistent atrial fibrillation (AF) despite having high recurrence and complication rates. Further options such as catheter ablation are considered once AF recurs. Patients with persistent AF undergoing catheter ablation are reported to have fewer symptoms and better quality of life than those undergoing DC cardioversion (DCCV) or optimal medical therapy. However, as yet this has not been subjected to a randomised, prospective, blinded clinical trial to measure the benefits of first-line AF ablation¹.

5.2 Purpose of the analyses

The aim of a future main clinical trial would be to investigate whether patients undergoing DC cardioversion (DCCV) with the addition of a pulmonary vein isolation (PVI) cardiac ablation procedure with cryoablation for atrial fibrillation (AF) will have lower rates of AF recurrence than those treated by DCCV without a cardiac ablation procedure. The trial will also assess symptoms, quality of life, functional status and treatment satisfaction. This pilot study aims to validate the key study logistics with a view to optimising the methods to be used in a future main trial and will also give an initial assessment of efficacy outcomes.

6 Study objectives and design

6.1 Design

ORBITA-AF feasibility study is an internal pilot study. It is a randomised blinded controlled trial at two sites. Patients will be randomised to receive DCCV+PVI or DCCV alone. No information about the procedure will be transferred from catheterisation laboratory (cath lab) staff to recovery staff and cath lab staff will have no further contact with the patient during the study. Patients and other healthcare professionals will remain blinded to treatment allocation. If a future trial is determined to be feasible and no major changes to the design have been made from this pilot study, then pilot study patients will be included in the future main trial. This pilot study aims to recruit 20 patients.

6.2 Study objectives

The main hypotheses to be tested in a full trial of this nature would be that AF ablation reduces the recurrence of persistent AF and improves quality of life compared to acute treatment of heart rhythm by cardioversion and best medical therapy. Through this pilot study, the main objective is to assess operational aspects of the trial in order to optimise methods for a future main trial. In addition, descriptive analyses of study outcome measures will also be undertaken.

6.3 Feasibility Endpoints

- Protocol non-adherence – (a) cross-over from one study group to the other, (b) do not receive randomised intervention.
- Recruitment rate (number recruited per month).
- Loss to follow-up at 12-months.
- Assessment of the success of the blinding procedure (i.e. blinding index).
- Data completeness.
- Key study logistics – especially around the delivery of the intervention, including the use of a 'chaperone' to maintain blinding.
- Identifying barriers and facilitators to implementation.
- Assessment of the feasibility of the blinding SOP.
- Assessment of the acceptability of the interventions.
- Descriptive assessment of outcome measures for main trial (as below).

6.4 Efficacy Endpoints

6.4.1 Primary endpoint

- Recurrence of Persistent AF (AF episode lasting > 7 days) within 12 months.

6.4.2 Secondary endpoints

- Death within 12 months.
- Hospital re-admission for any reason.
- Procedural-related complications.
- Bleeding events within 7 days of procedure.
- Requirement for repeat procedures within 12 months.
- Change in ejection fraction.
- Clinical success of procedure.
- Change in quality of life, as measured by SF-12 and AF-PROMS at 12 months.
- AF burden as measured on continuous monitoring.
- Antiarrhythmic drug use within 12 months.

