6.2 Secondary objective

The secondary objective of the trial will be to determine whether an early-ablation strategy is superior in terms of patient's quality of life than a cardioversion strategy, and to compare medication burden, cost efficacy and secondary endpoints of cardiac function (change in ejection fraction) between these strategies. Finally, the safety of the approaches will be compared.

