7.2 Exclusion criteria

Patients who meet the following exclusion criteria will be ineligible for study participation;

- Creatinine clearance (eGFR) < 30mls/min
- Contraindication or unable to take anticoagulation
- Contraindication or unable to tolerate amiodarone
- Uncontrolled hypertension
- Contraindication or catheter ablation
- BMI > 35

8. Study design

Barts Health patients referred from other Barts Health NHS Trust Hospitals (Homerton, Chase Farm, Barnet) for either cardioversion for persistent AF or catheter ablation of persistent AF will be approached for recruitment.

- All patients:
 - Patient drug treatment will follow local clinical guidelines for AF ablation and be recorded in the CRF.
 - Patient baseline characteristics recorded at preadmission
 - Estimated AF duration
 - LA dimensions (Echocardiogram)
 - Ejection fraction
 - Routine Bloods

- Creatinine & Electrolytes,
- Full blood count,
- Thyroid function
- Quality of Life measures
- BP
- CHADS VASC score / assessment
- Medical History and Comorbidities
- Demographics (Age, sex, ethnicity)
- Physical exam (BP, HR, Weight, Height, BMI)
- Medications
- Day of Procedure – blinded randomisation to intervention (DCCV, or Pulmonary Vein Isolation plus DCCV). Reveal LINQ inserted during procedure.
- 6 weeks: QoL measures, telephone FU
- 3 months: Clinical follow up, 12 lead ECG, Repeat QOL measures
- 12 months: Clinical follow up, Endpoints measured. Once subject participation in the trial is complete, the patient and physician will be unblinded. If the patient is in AF, management of AF proceeds as clinically indicated.
- All patients who consent to have data capture continue in AF registry for 5 years.

The pilot study patients will be analysed at 3 months and 12 months to allow assessment of feasibility of a larger trial, and patients who complete the 12 month follow-up visit and consent will continue in registry follow-up for 5 years post procedure.

9. Study procedures

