6.4.5 Assessment of primary and secondary efficacy endpoints

The primary endpoint is defined as the proportion of randomised patients with recurrent AF (AF episode lasting > 7 days) within 12 months, but outside of the initial 6-week blanking period (see section 8.1.2).

Secondary endpoints to be described are:

- Proportion dying within 12 months
- Proportion with hospital admission for any reason within 12 months
- Proportion with procedural-related complications defined as any AE that is deemed at least possibly related to intervention
- Proportion with bleeding events within 7 days of procedure
- Proportion with repeat procedures (any additional procedure for AF after the baseline index trial procedure(s)) within 12 months
- Change in ejection fraction from baseline at 12 months
- Proportion with clinical success of procedure
- Change in QoL at 12 months, as measured by SF-12 and AF-PROMS
- AF burden by 12 months
- Anti-arrhythmic drug use.

Clinical success will be defined as a 75% or greater reduction in the number of AF episodes as measured by the Reveal LINQ implant device within 12 months, but outside of the initial 6-week blanking period.

Change in QOL will be measured by the change in AF-PROMS summary scores and SF-12 PCS and MCS between screening and 12 months. SF-12 scores will be calculated as described in the appendix supplementary table 2³.

AF burden will be defined as the proportion of time in AF over the 12 months but outside of the initial 6-week blanking period, as measured by the Reveal LINQ implant device.

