DCCV + PCI	n12 (p12)	n22 (p22)	-
Don't know	n13 (p13)	n23 (p23)	-
Total	N1	N2	-
Blinding index	BI	BI	-

Table 3: Data completeness

	Treatment group		Total
	DCCV (N=)	DCCV +PVI (N=)	
Primary Endpoint data (Persistent AF)	N1 N2 % with data	N1 N2 % with data	N1 N2 % with data
SF12 3 months	N1 N2 % with data	N1 N2 % with data	N1 N2 % with data
12 months	N1 N2 % missing	N1 N2 % missing	N1 N2 % with data
AF-PROMS 3 months	N1 N2 % with data	N1 N2 % with data	N1 N2 % with data
12 months	N1 N2 % with data	N1 N2 % with data	N1 N2 % with data
Loop recorder interrogation performed			
3 months	N1 N2 % with data	N1 N2 % with data	N1 N2 % with data
12 Months	N1 N2 % with data	N1 N2 % with data	N1 N2 % with data
Patients completing all study assessments	N1 N2 % with data	N1 N2 % with data	N1 N2 % with data

N1= Number with data recorded

N2=Number with missing data

Table 4: Primary and Secondary Efficacy Endpoint analysis (ITT population)

	Treatment group		OR (80% CI)
	Placebo N=	Active N=	
Recurrent AF within 12 months	n/N (%)	n/N (%)	
Death within 12 months	n/N (%)	n/N (%)	
Hospital admission within 12 months	n/N (%)	n/N (%)	
Procedural-related complications	n/N (%)	n/N (%)	
Bleeding events within 7 days	n/N (%)	n/N (%)	
Requirement for repeat procedures within 12 months	n/N (%)	n/N (%)	
Clinical success of procedure	n/N (%)	n/N (%)	
AF drug use within 12 months	n/N (%)	n/N (%)	
	Placebo N=	Active N=	b (80% CI)
Change in ejection fraction at 12 months	Mean (SD)	Mean (SD)	
AF-Burden	Median [IQR] N Mean (SD)	Median [IQR] N Mean (SD)	
Change in QoL score at 12 months: SF-12 MCS	Mean (SD) N	Mean (SD) N	
SF-12 PCS	Mean (SD) N	Mean (SD) N	
AF-PROMS	Mean (SD) N	Mean (SD) N	

Table 5: Safety analysis – adverse events (safety population)

		Treatment group	
		Placebo N=	Active N=
Number of patients experiencing an AE within a year		n/N (%)	n/N (%)
Maximum severity AE experienced	Mild	n/N (%)	n/N (%)
	Moderate	n/N (%)	n/N (%)
	Severe	n/N (%)	n/N (%)
Total number of AEs across patients		n	n

Table 6: SAE listing

SAE number	Patient ID	SAE term (MedDRA)	SAE severity	Expected/ unexpected	Treatment group	Details of treatment	Related to treatment?
1							
2							
3							
4							
...							

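### Antiarrhythmic use is counted over the whole 12 months with no blanking, so periprocedural treatment encouraged in both arms dilutes any difference in later drug need

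*SAP*

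**What the plan says.** **The endpoint.** SAP 6.4.2 lists "Antiarrhythmic drug use within 12 months". SAP 6.4.5, which defines most of the other endpoints, has only "Anti-arrhythmic drug use", with no window, starting point or duration. Table 4 labels the row "AF drug use within 12 months" and gives n/N (%) per arm with an odds ratio. SAP 11.1.2 adds an 80% one-sided exact confidence interval for categorical endpoints.

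**Blanking.** SAP 6.4.5 leaves out the initial 6 weeks for the primary endpoint, clinical success and AF burden. It says nothing of the kind for drug use.

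**Background treatment.** Protocol 16.5 states: "Physicians will be encouraged to use anti-arrhythmic drugs in the periprocedural period". The example it gives is "in a reducing dose commencing at least 2 weeks prior to index procedure". It continues: "Participating centres will be encouraged to follow local centre periprocedural guidelines for antiarrhythmic medication for AF ablation for all patients". Protocol 8 likewise places drug treatment under local ablation guidelines for all patients, to be recorded in the CRF. Protocol 7.2 excludes patients with "Contraindication or unable to tolerate amiodarone".

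**The objective served.** Protocol 6.2 sets out to "compare medication burden, cost efficacy" and cardiac function between the two strategies. Protocol 5.3 suggests that an early PVI strategy may spare patients the side-effects of antiarrhythmics.

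**The concern.** A yes/no count over 12 months, read in the natural way, is ever-use. A patient who starts an antiarrhythmic two weeks or more before the procedure, and is still tapering on the day, is a yes at randomisation whichever arm is then drawn. That yes says nothing about whether PVI later reduced the need for drugs, which is what the medication-burden objective asks. The more patients who receive periprocedural treatment, the fewer are left in whom the arms can differ.

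At stake in the pilot is an uninformative row in Table 4. The larger stake is the main trial. SAP 6.3 makes a descriptive assessment of the main-trial outcome measures one of the feasibility endpoints, and SAP 6.1 brings the pilot patients into the main trial if the design is not changed in a major way. An endpoint definition left as it is could be carried forward with them.

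**Working it through.** The documents state no rate for antiarrhythmic use, so there is no figure of the plan's to reproduce on this point. The only design figure borrowed below is the main-trial size of 104 per group (Protocol 11.1). It does reproduce: HR = ln(1 − 0.66)/ln(1 − 0.47) = 1.70; Freedman's formula gives 117 events; 117/0.565/2 = 103.5, rounded up to 104.

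**Inputs**
- u: proportion given a periprocedural antiarrhythmic, equal in both arms because randomisation follows its start. Not stated, so varied from 0 to 100%.
- q: proportion using an antiarrhythmic later, after the blanking period. Not stated; assumed 60% for DCCV alone and 30% for DCCV+PVI, independent of periprocedural use.
- n: 10 per arm in the pilot (Protocol synopsis), 104 per arm in the main trial.

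**Formula**
- Ever-use in an arm = 1 − (1 − u)(1 − q).
- Difference between arms = (1 − u)(q for DCCV − q for DCCV+PVI).

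Example at u = 80%: DCCV 1 − 0.2 × 0.4 = 92%; DCCV+PVI 1 − 0.2 × 0.7 = 86%; difference 0.2 × 30 = 6 points.

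| Uptake u | DCCV | DCCV+PVI | Difference (points) | Power, 104 per arm | Chance that at least one pilot arm is 10/10 |
|---|---|---|---|---|---|
| 0% (later use only) | 60% | 30% | 30 | 99% | 0.6% |
| 50% | 80% | 65% | 15 | 68% | 12% |
| 80% | 92% | 86% | 6 | 28% | 56% |
| 90% | 96% | 93% | 3 | 16% | 83% |
| 100% | 100% | 100% | 0 | no contrast | 100% |

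Power is for a comparison of two proportions at the 5% level (taken as two-sided), with no allowance for loss or cross-over.

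**Other assumed rates.** With later use of 50% v 25%, the 25-point difference becomes 12.5 points at 50% uptake, 5 at 80% and 2.5 at 90%. Power at 104 per arm is 97% with no periprocedural use, then 49%, 19% and 11%.

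**The planned odds ratio at 10 per arm** (DCCV+PVI relative to DCCV)
- Later use only, 3/10 v 6/10: exact conditional odds ratio 0.31, 80% one-sided upper limit 0.95.
- Ever-use of 9/10 v 10/10: odds ratio 0, upper limit 4.0.
- Ever-use of 10/10 v 10/10: odds ratio undefined, interval 0 to infinity.

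**Independence.** Without this assumption the factor (1 − u) still applies, but to the between-arm difference in later use among patients who had no periprocedural drug. The documents do not say how large that difference is.

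**The case against.** A reader might infer that both arms will sit near 100% and that the medication-burden objective cannot be answered. The documents do not support either statement.

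- **Uptake is unknown.** Use is encouraged, not required, and the choice of drug is left to the patient's physician. The amiodarone exclusion shows that patients could take that drug, not that they do. On the assumed rates, a ceiling in both arms needs uptake of roughly 90% or more, which the text neither states nor rules out. At 50% uptake the arms would be 80% v 65%: diluted, but not at a ceiling.
- **Ever-use is a reading.** It is the natural one for the Table 4 row, but the SAP does not say whether drugs begun before the procedure count.
- **The data may be recoverable.** Drug treatment goes on the CRF (Protocol 8 and 16.5), so a better measure could be derived if follow-up use and dates are recorded.
- **This is a pilot.** SAP 6.5 rules out hypothesis tests, and 10 patients per arm would not settle a medication comparison under any definition. Finding near-universal use would itself be a useful pilot result.

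All of this stands as a limit on the strength of the claim. It does not remove the defect. Dilution does not depend on reaching a ceiling: half the difference is lost at 50% uptake. That the CRF might support a better measure is a reason to define it now.

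**Conclusion.** The point holds as a weakness of definition. The 12-month yes/no count is not blanked, and it combines periprocedural treatment encouraged alike in both arms with the later drug need that the objective concerns. A between-arm difference in later use shrinks by the factor (1 − uptake): from 30 points to 15, 6, 3 or 0 at uptake of 50%, 80%, 90% or 100%. Those figures rest on assumed later use of 60% v 30%, equal uptake in the arms and independence of the two. The direction does not depend on the particular rates; the size does.

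The endpoint is therefore a weak measure of medication burden, and it may approach a ceiling if uptake is about 90% or more. That the ceiling will occur, or that the objective is beyond reach, does not follow from the documents. The consequence in the pilot is limited to one descriptive row; the main reason to act is that the definition could pass unchanged into the main trial.

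**What to change.** In SAP 6.4.2, 6.4.5 and Table 4, under one consistent label:

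1. Define the endpoint as any antiarrhythmic use after the 6-week blanking period and up to 12 months, in line with the blanking already applied to recurrence, clinical success and AF burden.
2. Add a row for antiarrhythmic use at the 12-month visit.
3. Report periprocedural use by arm as a separate descriptive row. This also supplies the uptake figure that the main trial will need.
4. Confirm that the CRF captures antiarrhythmic start and stop dates at follow-up. Both assessment schedules (Protocol 9.4 and SAP 6.4.3) name medications only at screening, although Protocol 8 and 16.5 say that drug treatment is recorded.

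**Cost.** SAP wording, two additional table rows and possibly a small CRF addition. One limitation remains: a taper that runs past week 6 still counts in the first measure, which is why the 12-month row is added. The change concerns measurement only. It alters no treatment and takes no position on any drug or schedule.
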